4.2.1.4. Time-to-response

Time (months) to response (TTR) by RECIST is defined as the time from start of study treatment until the date of first documented objective response, either confirmed CR or confirmed PR (whichever status is recorded first), according to RECIST v1.1. It will be calculated for patients whose BOR is either confirmed CR or confirmed PR.

TTR by RANO is defined as the time from start of study treatment until the date of first documented objective response, either CR or PR or MR (whichever status is recorded first), according to RANO. It will be calculated for patients whose BOR is either CR or PR or MR.

TTR is calculated as (date of first occurrence of CR or PR or MR – date of start of study treatment + 1)/30.4375.

4.2.1.5. Progression-free Survival

PFS is defined as the time (months) from the date of first administration of study treatment until the first radiographic documentation of objective progression as assessed by investigator using RECIST v1.1 or RANO criteria for glioma patients, or death from any cause.

More specifically, PFS will be determined using all the assessment data up until the last evaluable

visit prior to or on the date of

- (i) disease progression as defined by RECIST Version 1.1 or RANO or death; or
- (ii) withdrawal of consent or lost to follow-up; or
- (iii) receiving subsequent anti-cancer medication, whichever is earlier.

Patients without report of PD or death from any cause at the time of analysis are censored as described in [Table 5](#) below.

The PFS time will always be derived based on scan dates not tumor assessment dates. RECIST or RANO assessments/scans contributing towards a particular visit may be performed on different dates. The following rules are applied:

- Date of progression is determined based on the earliest of the dates of the component that triggered the progression.
- When censoring a patient for PFS, the patient is censored at the latest of the dates contributing to a particular overall visit assessment.

Table 5 Outcome and Event or Censoring Dates for PFS

Rule	Situation	Date of Progression or Censoring	Outcome
1	PD documented from radiological assessment visits	Date of first documented disease progression	Event
2	Death without PD or death after one missing radiological assessment visit	Date of death	Event
3	No baseline nor post-baseline radiological assessments available	Date of first administration of study treatment	Censored
4	No death or PD by the time of data cut-off for analysis	Date of last adequate radiological assessment	Censored
5	Early discontinuation (lost to follow-up or withdrawal of consent) of study without death or PD	Date of last adequate radiological assessment	Censored
6	New anti-tumor therapy started prior to PD	Date of last adequate radiological assessment prior to or on date of initiation of new therapy visit	Censored
7	Death or PD after two or more consecutive missed or inadequate radiological assessment visits	Date of last adequate radiological assessment prior to missed visits	Censored

Note: An adequate radiologic assessment is defined as an assessment where the Investigator determined radiological response is CR, PR, SD, or PD. If PD and new anti-cancer medication occur on the same day, will assume that the progression was documented first, e.g. outcome is progression and the date is the date of the assessment of progression

Note: The same algorithm for determination of two or more consecutive missing or inadequate assessments can be found in [Section 4.2.1.3](#).

PFS is calculated as (date of progression or censoring as per rules in [Table 5](#) – date of first administration of study treatment + 1)/30.4375. Reasons for censoring are included in [Table 6](#) following the hierarchy.

Table 6 PFS Censoring Reasons and Hierarchy

Hierarchy	Condition	Censoring Reason
1	No baseline nor post-baseline tumor assessments available	No baseline nor post-baseline tumor assessments
2	New anti-tumor therapy started prior to PD	New anti-tumor therapy started prior to PD
4	Two or more consecutive missed or inadequate radiological assessment visits	Two or more consecutive missed or inadequate radiological assessment visits
5	Drops out before end of study, no progression or death, lost to follow-up	No death nor PD, lost to follow-up
6	Drops out before end of study no progression or death, withdrawal by subject from the study	No death nor PD, withdrawal by subject
7	No death nor PD by the time of data cut-off for the analysis	No death nor PD by the time of data cut-off for the analysis

4.2.2. Exploratory Endpoint

4.3. Exposure Endpoints

Duration of Exposure

Patients will receive dosing of HMPL-306 PO, QD, in each 28-day cycle.

In dose escalation, dose will begin at **CC1** mg QD of HMPL-306 in a 28-day continuous dosing treatment cycle. The dose will escalate successively according to the sequence of **CC1** mg QD, **CC1** mg QD, **CC1** mg QD, **CC1** mg QD, **CC1** mg QD, **CC1** mg QD, and **CC1** mg QD.

In dose expansion, HMPL-306 will be administered PO, QD, in a 28-day continuous dosing treatment cycle at MTD and/or RP2D.

The duration of exposure (days) = Last dose date of non-zero study drug – first dose date of non-zero study drug + 1.

The actual duration of exposure (days) = Cumulative days with non-zero study drug administered.

Dose Intensity and Cumulative Dose

Algorithms for calculating parameters relevant to the dose exposure and intensity are included in [Table 7](#).

Table 7 Algorithms for Calculating Parameters Relevant to the Dose Exposure and Intensity

Parameter	HMPL-306 CC1 mg [§]
Dosing schedule per protocol	PO, QD, each day in a 28-day treatment cycle
Cumulative dose (mg)	Sum of the doses administered to a patient in the duration of exposure
Dose intensity (mg/day)	Cumulative dose (mg) / (duration of exposure)
Relative dose intensity (RDI) (%)	100 * [Dose intensity (mg/day) / (CC1) (mg/day)]

§ Different doses (e.g. **CC** mg PO QD, **CC** mg PO QD) of HMPL-306 may be evaluated. The calculation of relevant parameters will be adjusted accordingly based on the example presented in this table.

PO = *Per os* (oral administration); QD = *Quaque die* (once daily)

In addition, the RDI (%) will be categorized to the groups: < 50%; 50 - < 70%; 70 - < 90%; 90 - < 110%; ≥ 110%.

Dose Interruptions, and Dose Reductions

- Dose interruption and dose reductions are all based on the dose administration data, the associated reasons for each of them include categories: (1) Adverse event, (2) DLT, and (3) Other.
- Dose modifications of study drug include dose interruption and dose reduction.

4.4. Safety Endpoints

The safety analysis set is used to evaluate the safety variables including AEs, clinical laboratory data, vital signs, single 12-lead ECG parameters, ECHO/MUGA parameters, physical examinations, ECOG performance status, and death. The safety data during the treatment period will be summarized, and the treatment period is defined as the duration from the date of the first study drug administration until 30+7 days (7-day window only applied to parameters collected by visit) after last dose or prior to the start of a subsequent anti-tumor therapy (whichever comes first). Dose Limiting Toxicities (DLTs)

AEs will be assessed per the DLT criteria during the 28-day DLT assessment window in Cycle 1 for study Part 1, which starts with the first day of administration of study drug. .

4.4.1. Adverse Events (AEs)

All AEs will be coded from verbatim text to preferred term (PTs) and grouped by system organ class (SOC) using the Medical Dictionary for Regulatory Activities (MedDRA) version 27.1. AEs will be graded by investigator according to NCI CTCAE v5.0. Missing severity grade will not be imputed.

An AE is considered a TEAE:

(i) If one of the criteria is met:

1. If the onset date is on or after the start of study treatment until 30 days after the last dose or prior to the start of a subsequent anti-tumor therapy (whichever comes first), or if the onset date is missing; or
2. If the AE has an onset date before the start of study treatment, but worsened in severity after the study drug administration (i.e. SAE start date is on or after the start of study treatment until 30 days after the last dose or prior to the start of a subsequent anti-tumor therapy (whichever comes first));

(ii) Beyond 30 days after the last dose or after the start of a subsequent anti-tumor therapy (whichever comes first), treatment-related SAEs will also be considered as TEAEs.

Investigator assessed AEs causality to study drug will be classified as "Related" and "Not Related". An AE with a missing causality will be classified as "Related" to study drug.

Other AE variables include drug-related AEs, COVID-19 related AEs, AEs leading to study drug modifications (i.e. dose interruption, dose reduction, or study drug withdrawal), AEs leading to death, and SAEs.

For AEs which are not on-going, duration of AE (days) is defined as AE end date – AE start date +1; for on-going AEs, the end date will be listed as ‘Ongoing’.

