8.7.3 Persistent or Recurrent Adverse Events

A persistent AE is one that extends continuously, without resolution between subject evaluation time points. Such events should only be recorded once in the eCRF unless the severity changes. If a persistent AE becomes more or less severe, it should be recorded again in a new eCRF entry. Please refer to the eCRF Completion Guidelines for information on completing each eCRF.

A recurrent AE is one that occurs and resolves between subject evaluation time points and subsequently recurs. All recurrent AEs should be recorded on the eCRF.

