List of Figures

Figure 1	Study Schema.....	12
----------	-------------------	----

LIST OF ABBREVIATIONS

Abbreviation	Term
AE	adverse event
ATC	anatomic therapeutic classification
BMI	body mass index
BOR	best overall response
CFB	change from baseline
CI	confidence interval
COVID	coronavirus disease 2019
CR	complete response
CSR	clinical study report
CTCAE	Common Terminology Criteria for Adverse Events
DBL	database lock
DBP	diastolic blood pressure
DCR	disease control rate
DLT	dose-limiting toxicity
DoR	duration of response
ECG	electrocardiogram
ECHO	echocardiogram
ECOG	Eastern Cooperative Oncology Group
EOT	end of treatment
GCP	Good Clinical Practice
HG	hydroxyglutaric acid
ICF	inform consent form
ICH	International Council on Harmonization
IDH	isocitrate dehydrogenase
IV	intravenous(ly)
LLQ	lower limit of quantification
MedDRA	Medical Dictionary for Regulatory Activities
MR	minor response
MUGA	multiple-gated acquisition
NCA	non-compartmental analysis
NCI	National Cancer Institute
MTD	maximum tolerated dose
NET	neuroendocrine tumor
ORR	objective response rate

Abbreviation	Term
OS	Overall survival
PD	progressive disease
PD-L1	programmed death-Ligand 1
PFS	progression-free survival
PK	pharmacokinetic
PO	oral(ly)
PR	partial response
PT	preferred term
QD	once daily
QTcF	QT interval corrected by the method of Fredericia
RANO	Response Assessment in Neuro-Oncology
RECIST 1.1	Response Evaluation Criteria in Solid Tumors, Version 1.1
RP2D	recommended Phase 2 dose
SAE	serious adverse event
SAP	statistical analysis plan
SBP	systolic blood pressure
SD	stable disease
SMQ	standardized MedDRA queries
SOC	system organ class
SRC	Safety Review Committee
TEAE	treatment-emergent adverse event
TLF	table, listing, figure
TPR	timepoint response
TTR	time to response
WHO-DD	World Health Organization Drug Dictionary

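### SAP 4.4.1 defines worsening in severity by the SAE start date, so the second TEAE criterion tests seriousness instead of grade

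*SAP*

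**What the plan says.** SAP 4.4.1 gives two in-window routes by which an AE becomes a TEAE, and one late route.

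- Criterion (i)1 looks at onset: "If the onset date is on or after the start of study treatment until 30 days after the last dose", or before a subsequent anti-tumor therapy if that comes first. A missing onset date also qualifies.
- Criterion (i)2 covers an AE with onset before treatment "but worsened in severity after the study drug administration". A parenthesis introduced by *i.e.* gives the test: "SAE start date is on or after the start of study treatment", up to 30 days after the last dose and again cut off by a new therapy.
- Criterion (ii) applies after the window: "treatment-related SAEs will also be considered as TEAEs".

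The SAP's abbreviation list expands SAE only as "serious adverse event". On severity, SAP 4.4.1 says "AEs will be graded by investigator according to NCI CTCAE v5.0". For recording, protocol 8.7.3 states: "If a persistent AE becomes more or less severe, it should be recorded again in a new eCRF entry". It refers to the eCRF Completion Guidelines for entry instructions and does not give the start date of the new entry.

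**The concern.** The two halves of criterion (i)2 describe different things. Protocol 8.1.2 defines seriousness by outcome (death, hospitalization and so on), whereas protocol 8.5 defines severity by CTCAE grade. SAP 5.2.11.2 keeps them apart too, with separate summaries for Grade 3 or higher TEAEs and for serious TEAEs. An AE can rise from Grade 1 to Grade 3 without ever having an SAE start date, and an AE can become serious without a change of grade.

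TEAEs are part of the primary safety endpoint (SAP Table 1), and most of the AE summaries in SAP 5.2.11.2 are restricted to them. A programmer who codes the parenthesis as written implements a rule that disagrees with the sentence it is meant to explain.

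**Working it through.** The plan gives no figure to reproduce, so the check applies the rule as written to the possible cases and compares the result with the lead wording of (i)2. Each case starts from an AE with onset after consent and before first dose. Criterion (ii) helps in none of them, because it covers only related SAEs after the window.

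| Case | (i)1 | (i)2, literal test | Result | Lead wording of (i)2 |
|---|---|---|---|---|
| a. Grade 1 to 3 on drug, never serious, original onset kept | fails | fails: no SAE start date | not a TEAE | TEAE |
| b. Grade 1 to 3 on drug, becomes serious in the window, original onset kept | fails | passes | TEAE | TEAE |
| c. As a, but the new entry is dated at the change | passes | fails | TEAE, through (i)1 | TEAE |
| d. Serious before first dose, grade rises on drug, original onset kept | fails | fails: SAE start date is pre-dose | not a TEAE | TEAE |
| e. Becomes serious on drug, no grade rise | fails | passes | TEAE on the literal test | not a TEAE |

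**Dependence on the record date.** Cases a and c are the same clinical event. They differ only in the start date of the entry required by protocol 8.7.3. With the original onset, the event drops out of the TEAE tables. With the change date, (i)1 counts it and (i)2 adds nothing for severity.

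**Could SAE be a slip for AE?** Possibly, but the substitution alone does not repair the clause. It would then require an onset before treatment and an AE start date on or after treatment, which a single record cannot satisfy. It works only if it means the start of a separate, worsened record, and the SAP does not say so.

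**Which events are exposed.** AEs are collected from the main consent (protocol 8.2.1), and screening runs up to 28 days before first dose (protocol 6.1.2). Conditions already present at Screening go to medical history and become AEs only if they worsen (protocol 8.7.5). Such an AE is first recorded because of the worsening and would ordinarily have an on-treatment onset, so it would meet (i)1. The exposed group is therefore mainly AEs that arise between consent and first dose and then worsen non-seriously.

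**Size.** The documents give no rate of pre-dose AEs and no rate of worsening, so no count can be derived. What can be shown is the weight of one patient. Part 1 expects about 27 to 36 patients over eight dose levels, and results are shown by dose level (SAP 2.3.1 and 5.1.1). If they are spread evenly, which is an assumption, that is 27/8 = 3.4 to 36/8 = 4.5 per level. One reclassified patient then moves a column by 1/4.5 = 22 to 1/3.375 = 30 percentage points. This is the sensitivity of the display to one patient; it does not estimate how many patients are affected.

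**The case against.** The strongest reply is that the recording rules already handle the problem. The natural reading of protocol 8.7.3 is that a new entry starts when the severity changes. An entry with the old onset would show one AE at two grades over the same dates and distort the duration that SAP 4.4.1 calculates from each record's start and end dates. On that reading (i)1 counts the event and nothing is lost. All AEs are also listed with dates and grade whether or not they are TEAEs (SAP 5.2.11.2), and the laboratory and ECOG shift tables do not depend on TEAE status.

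Much of this stands, and it rules out stronger readings. A reader might infer that TEAEs are certainly under-counted. The documents do not show that, because it depends on a dating convention set in guidelines that were not supplied. A reader might infer that any error can only lower the counts, but case e goes the other way. A reader might also infer that baseline symptoms made worse by the drug vanish as a class, but protocol 8.7.5 sends most of them through (i)1.

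What the reply does not do is make (i)2 correct. Under the natural reading the clause is unnecessary for severity and still tests the wrong attribute; under the other reading it loses events. No other text in the SAP repairs it, including Section 7 on changes from the protocol, and the supplied protocol contains no TEAE definition to fall back on.

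**Conclusion.** Criterion (i)2 is wrong as written: it states a severity rule and applies a seriousness test. That conclusion rests on the text alone. The effect on TEAE counts is conditional on the start date of the new entry and may be nil. If events are lost, they are mainly AEs arising between consent and first dose that worsen without becoming serious, and their number cannot be derived from the documents.

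Nothing here supports a claim that dose decisions were affected; the Safety Review Committee makes those (SAP 6.1). One limit on the check is that the SAP is based on Protocol Amendment 3 and the supplied protocol is Amendment 2, so a TEAE definition or recording rule in the later amendment could not be examined. The correction should be made because it concerns a primary-endpoint derivation and costs very little.

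**What to change.** Replace the parenthesis in SAP 4.4.1 (i)2 with a test on the worsened record, for example: *i.e. a record of the same AE that starts on or after first dose, inside the same 30-day or new-therapy window, has a CTCAE grade higher than the last grade before first dose*. This uses start date and grade, both of which are among the AE variables listed in SAP 5.2.11.2; no separate grade-change date appears there.

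Also confirm in the eCRF Completion Guidelines that the new entry for a severity change starts on the date of the change. Without that, the revised test would have no post-dose record to find.

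One consequence should be settled at the same time. Protocol 8.7.3 also asks for a new entry when an AE becomes less severe, and (i)1 contains no grade comparison. A pre-dose AE that improves on drug would then also satisfy (i)1 through its new entry, so the SAP should say whether the grade comparison governs continuation records there too.

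The cost is one SAP sentence, the matching programming condition and a check of the guidelines. If existing entries do not follow the dating convention, their start dates would need a data query.

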4.4.2. Laboratory

Blood and urine samples for the determination of clinical chemistry, hematology, and urinalysis laboratory variables described in Table 8 will be measured.

Table 8 Laboratory Assessment

Lab Category	Lab tests
Hematology	hemoglobin, hematocrit, red blood cell count (RBC), white blood cell count (WBC), platelet counts, ARC, Reticulocyte %, ANC, Neutrophils %, ALC, Lymphocytes %, Monocyte Absolute, Monocytes %, Basophil Absolute, Basophils %, Eosinophil Absolute, Eosinophils%, and other non-protocol specified tests
Chemistry	albumin, Alkaline Phosphatase (ALP), total bilirubin, direct bilirubin, indirect bilirubin, calcium, magnesium, chloride, creatinine, creatine phosphokinase, glucose, inorganic phosphorus, potassium, total protein, Alanine Aminotransferase (ALT), Aspartate Aminotransferase (AST), Lactate Dehydrogenase (LDH), sodium, and Blood Urea Nitrogen (BUN), and other non-protocol specified tests
Blood amylase and lipase	amylase, lipase
Fasting lipid panel	Total Cholesterol, High-density Lipoprotein, Low-density Lipoprotein, Triglycerides
Coagulation	Activated Partial thromboplastin time (aPTT), Prothrombin time (PT), International normalized ratio (INR)
Urinalysis	semiquantitative dipstick: evaluation of glucose, protein, RBC, WBC, Ketone body, Urobilinogen

Change from baseline in laboratory test results to each assessment will be calculated. The non-protocol specified scheduled tests will not be summarized; they will only be included in listings. Data recorded by the laboratory will be converted to the International System of Units (SI) and all presentations will use SI units. Quantitative laboratory measurements reported as “< X”, i.e. below the lower limit of quantification (LLQ), or “> X”, i.e. above the upper limit of quantification (ULQ), will be converted to X for the purpose of quantitative summaries, but will be presented as recorded, i.e. as “< X” or “> X” in the listings.

Clinical laboratory results will be graded according to NCI CTCAE criteria, Version 5.0 which can be found in [Appendix 1](#). Any assessment for which CTCAE toxicity grades are not available, will not be included in any analyses for which toxicity grades are required. Grade 0 is assigned to all laboratory values except missing values and not already assigned another grade. Missing values are considered missing.

Analysis of Abnormal Hepatic Laboratory Values

The following categories of abnormal hepatic laboratory values will be evaluated for any occurrence among all assessments in treatment period.

- Aspartate aminotransferase (AST) > 3,5,8,10, and 20x ULN
- Alanine aminotransferase (ALT) > 3,5,8,10, and 20x ULN
- AST and/or ALT > 3,5,8,10, and 20x ULN
- Total bilirubin elevations > 1.5x, >=2x ULN
- ALP > 1.5x, 2 x ULN
- AST and/or ALT > 3x ULN and (total bilirubin > 1.5x, >=2x ULN) [defined as at least one total bilirubin > 1.5x, >= 2x ULN within 14 days after ALT or AST > 3x ULN]
- Hy's Law criteria: AST and/or ALT > 3x ULN and total bilirubin ≥ 2x ULN and ALP < 2x ULN [defined as at least one total bilirubin >= 2x ULN and all ALP < 2x ULN within 14 days after ALT or AST > 3x ULN]

Additionally, the minimum, and maximum values for each patient over the entire treatment period for each quantitative laboratory parameter will also be derived. The change from baseline will also be calculated using these minimum and maximum values.

All laboratory results in SI units are presented in data listings.

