Visit Frequency	
Cycle 1: every week (±1 day, except D1)
 
Cycle 2: every 2 weeks (±1 day)
 
Cycle 3 and onward: Day 1 (±3 days)
 
End of Treatment: within 7 days (±3 days) after the last dose
 
For Cohort C-1:
 
Pre-surgery: every week (±1 day, except D1)
 
Cycles 1 and 2: every 2 weeks (±3 days)
 
Cycle 3 and onward: Day 1 (±3 days)
 
End of Treatment: within 7 days (±3 days) after the last dose

Number of Participants	
Part 1: at least 1 subject will be enrolled to dose levels 1, 2, and 3. At least 3 subjects will be enrolled to dose levels 4, 5, 6, 7, and 8.
 
Part 2: approximately 20 evaluable subjects (15 subjects in Cohort C-1) per cohort will be enrolled; for a total of approximately 95 subjects

Intervention Groups and Duration	
Part 1: CCI, and CCI mg of HMPL-306 PO QD administered to dosing groups for 28 days cycles
 
Part 2: MTD/RP2D as determined in Part 1, administered PO QD to approximately 95 subjects for 28-day cycles

Data Monitoring/Other Committee	Yes

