7.4.2 Dose Adjustment Outside the DLT Assessment Window (Including Dose Expansion Part)

Table 7 Dose Adjustment for Hematologic Toxicity

CTCAE v5.0 Grade	Action
Grade 1 or 2	None
Grade 3 or 4 (believed to be related to HMPL-306 and NOT underlying disease)	
 • Hold drug. • If the toxicity improves to Grade ≤ 2 within 28 days, then resume at original dose. • If the toxicity recurs at original dose, then resume at 1 dose lower provided the toxicity improves to Grade ≤ 2 within 28 days. • If the toxicity recurs in setting of prior dose level reduction, then resume at the next lower dose provided the toxicity improves to Grade ≤ 2 within 28 days. • In the event the toxicity does not improve to Grade ≤ 2 within 28 days or toxicity recurs despite 2 dose reductions, HMPL-306 treatment is to be permanently discontinued.

AE = adverse event; CTCAE v5.0 = Common Terminology Criteria of Adverse Events version 5.0.

Table 8 Dose Adjustment for Non-Hematologic Toxicity

CTCAE v5.0 Grade	Action
Grade 1 or 2	None
Grade 3 ¹	
 • Hold drug. • If the toxicity improves to Grade ≤ 2 within 28 days then resume at original dose. • If the toxicity recurs at original dose, then resume at 1 dose lower provided the toxicity improves to Grade ≤ 2 within 28 days. • If the toxicity recurs in setting of prior dose level reduction, then resume at the next lower dose provided the toxicity improves to Grade ≤ 2 within 28 days. • In the event the toxicity does not improve to Grade ≤ 2 within 28 days or toxicity recurs despite 2 dose reductions, HMPL-306 treatment is to be permanently discontinued.
Grade 4 ¹	
 • Permanently discontinue treatment with HMPL-306.

CTCAE v5.0 = Common Terminology Criteria of Adverse Events version 5.0.

1. Dose adjustments or modifications for Grade ≥ 3 nausea, vomiting, diarrhea, constipation, fatigue, and electrolyte imbalance are not required if they can be controlled by systemic or local drug administration.

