2.2. Study Design

[figure not shown]
This is a phase 1, open-label, multicenter study to evaluate the safety and tolerability of HMPL 306 administered orally (PO) in treatment of patients with locally advanced or metastatic solid tumors with IDH mutation. The study consists of 2 parts: Part 1 (dose escalation) and Part 2 (dose expansion). Only part 1 included in this analysis plan.

The first part of the study is dose escalation where cohorts of patients will receive ascending oral doses of HMPL-306 to determine maximum tolerated dose (MTD) and/or the recommended phase 2 dose (RP2D). The modified toxicity probability interval-2 (mTPI-2) (Yang et al, 2015) design will be utilized. The mTPI-2 method uses a Bayesian framework and a hierarchical model to compute the dose escalation based on the interval between the toxicity rate of each dose level and target probability (Guo et al, 2017). This study is designed targeting a dose-limiting toxicity (DLT) rate of 25% with an equivalence interval of 20% to 30%.

A cycle of study treatment is defined as 28 days of continuous daily dosing, according to the cohort and dose level. At the starting dose, patients will be administered HMPL-306 at [REDACTED] mg PO, QD, and the dose will escalate successively according to the sequence of [REDACTED] mg QD, [REDACTED] mg QD, [REDACTED] mg QD, [REDACTED] mg QD, [REDACTED] mg QD, [REDACTED] mg QD, and [REDACTED] mg QD.

The overall study schema of part 1 is presented in Figure 1

Figure 1 Study Schema

Subjects who complete the DLT assessment window and are deemed by the investigator to be benefiting from HMPL-306 treatment will be allowed to continue treatment until disease progression, intolerable toxicity, at the investigator's discretion that the subject can no longer

benefit from the study treatment, withdrawal of consent, lost to follow-up, the end of study, or death, whichever comes first.

Safety Follow-up

Subjects who have completed the study treatment will be evaluated for safety 30 days (± 7) days following the EOT visit for study drug-related AEs until resolution and SAEs until resolution regardless of relationship to study treatment.

Efficacy Follow-up

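### From Cycle 3 the SAP's 14-day liver-signal window does not reach the next Day 1 chemistry draw, so some sequential ALT/AST-then-bilirubin rises are not paired

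*SAP*

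**What the plan says.** SAP 4.4.2, under abnormal hepatic laboratory values, defines two combined categories. One is ALT and/or AST >3x ULN with total bilirubin >1.5x or >=2x ULN. The other is Hy's Law, which adds an ALP condition. Both look forward a fixed time from the transaminase rise: the first ends "2x ULN within 14 days after ALT or AST > 3x ULN", and the second requires "all ALP < 2x ULN within 14 days after ALT or AST > 3x ULN". The categories "will be evaluated for any occurrence among all assessments in treatment period", so unscheduled and EOT panels count as well as cycle visits.

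The schedule comes from the protocol. The Synopsis gives visits as "Cycle 1: every week (±1 day, except D1", then "Cycle 2: every 2 weeks (±1 day", then "Cycle 3 and onward: Day 1 (±3 days". Table 1 places blood chemistry at these visits (in Cycle 1 from D8, with baseline chemistry at screening), at EOT and at Safety Follow-up. SAP 2.2 confirms the cycle length: "A cycle of study treatment is defined as 28 days of continuous daily dosing". ALT, AST, ALP and bilirubin belong to one chemistry panel (Table 1, footnote 10). Unscheduled examinations are allowed if clinically indicated (footnote 6). No supplied text requires a repeat liver panel by a set date after a transaminase rise.

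**The concern.** The definitions are written to catch a bilirubin rise that follows a transaminase rise. That works only if a bilirubin value exists inside the look-ahead. Once chemistry moves to one draw per 28-day cycle, a 14-day look-ahead ends before the next cycle draw is due.

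This matters because abnormal hepatic function is the only adverse event of special interest listed in SAP 5.2.11.2, and it is a named potential risk in protocol Table 3. These two categories are also the only SAP displays that link ALT/AST to bilirubin over time. The other hepatic rows and the per-patient minimum and maximum are computed one analyte at a time, and SAP 5.2.11.4 plans no joint display. A patient whose transaminases rise at one visit and whose bilirubin rises at the next could be absent from both combined rows.

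**Working it through.** There is no stated figure to reproduce. The check compares the gap between scheduled draws with the 14-day window.

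**Inputs.** Window: 14 days (SAP 4.4.2). Cycle: 28 days (SAP 2.2). Visit windows: ±1 day in Cycles 1 and 2 (except C1D1) and ±3 days from Cycle 3 (protocol Synopsis; Table 1, footnote 6). EOT: within 7 days (±3) after the last dose, read here as 0 to 10 days. Safety Follow-up: 30 ± 7 days after EOT.

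**Formula.** Gap range = nominal gap ± (window of first visit + window of second visit). Each visit window is taken around its scheduled date. The share inside is the count of whole-day combinations with gap ≤14.

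| From → to | Calculation | Range (days) | Combinations ≤14 days |
|---|---|---|---|
| Cycle 1 weekly draws, to C2D1 | 7 ± (1+1) | 5 to 9 | 9 of 9 |
| C2D1 → C2D15 | 14 ± (1+1) | 12 to 16 | 6 of 9 |
| C2D15 → C3D1 | 14 ± (1+3) | 10 to 18 | 12 of 21 |
| C3D1 onward, Day 1 → Day 1 | 28 ± (3+3) | 22 to 34 | 0 of 49 |
| EOT → Safety Follow-up | 30 ± 7 | 23 to 37 | 0 of 15 |

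**EOT after a Day 1 draw.** If the last dose is k days after the draw, EOT falls k to k+10 days after it.
- k = 0 to 4: always inside 14 days (4+10 = 14).
- k = 5 to 14: sometimes inside.
- k = 15 or more: never inside.

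**Same panel.** The gap is 0 days. It is inside the window if the SAP's wording includes day 0, which it does not state.

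**Two constructed records, with ALP normal throughout and no EOT or unscheduled panel between visits:**
- C4D1: ALT 4x ULN, bilirubin normal. C5D1: bilirubin 2.5x ULN, ALT and AST at or below 2.5x ULN. Neither combined row is met.
- Same C4D1. C5D1: bilirubin 2.5x ULN, ALT 3.5x ULN. Both rows are met through the C5D1 panel itself, if day 0 counts.

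**How much treatment is affected.** Cycle 3 starts on day 57 (2 × 28 + 1). The share of treatment beyond day 56 depends on time on drug, which the documents do not give. Two assumed durations show the range:
- 2.7 months, the median PFS the protocol cites for another IDH inhibitor in cholangiocarcinoma: 2.7 × 30.4375 = 82 days; (82 − 56)/82 = 32%.
- 18 months, the SAP's last example PFS landmark: 18 × 30.4375 = 548 days; (548 − 56)/548 = 90%.

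**The case against.** The strongest reply is that the gap is narrow. Any ALT/AST >3x ULN opens a window, so a patient whose transaminases are still raised at the next visit is captured there. EOT carries chemistry and can fall inside 14 days when dosing stops soon after the abnormal draw. The rule uses all assessments, and a worrying result would often prompt an unscheduled panel. All of this stands. A reader might infer from the 28-day schedule that a next-visit bilirubin rise can never count, or that sequential cases are zero by construction. The documents do not support either reading: only cases with both ALT and AST back to ≤3x ULN, and no qualifying panel within 14 days, are lost.

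A reader might also cite protocol Table 8, "Dose Adjustment for Non-Hematologic Toxicity", because its action for Grade 1 or 2 is none. That table governs dosing, not repeat testing, and does not show that no recheck would occur.

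It can also be said that nothing is hidden. The first constructed patient appears in the ALT >3x row, the bilirubin >=2x row, the grade shifts and the listings. Hepatic events are searched separately by SMQ. With about 27 to 36 subjects, no formal testing and Part 1 only, the listings can be read by hand. This lowers the stakes, but none of those displays pairs the two values, so the combined rows could still understate the count.

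Finally, window length is partly a choice, and a short window has merit in demanding near-concurrence. That is a reason to keep the 14-day rows, not a reason to omit a longer one.

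**Conclusion.** The point holds in limited form. From Cycle 3, none of the 49 compliant visit-window combinations puts the next Day 1 draw within 14 days; the shortest gap is 22 days. The same is true from EOT to Safety Follow-up (shortest 23 days). In Cycle 2 the result depends on where visits fall in their windows (6 of 9 and 12 of 21 combinations inside). Cycle 1 is covered. How many patients would be missed cannot be estimated from the documents.

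The conclusion rests on three assumptions:
- Day 0 is included in the 14 days.
- Visit windows are measured from scheduled dates.
- The chemistry schedule is unchanged in Protocol Amendment 3, on which the SAP is based; the protocol supplied is Amendment 2. For the same reason, the absence of a required repeat panel is established only for Amendment 2.

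This is a cheap improvement to a descriptive safety summary, not a flaw that undermines the analysis.

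**What to change.** In SAP 4.4.2:
1. Keep the 14-day rows for both combined categories and state that day 0 is included.
2. Add one row per category with a 34-day window, the longest compliant gap between Day 1 draws (28 + 3 + 3).
3. In the added Hy's Law row, require ALP <2x ULN both at the ALT/AST elevation and in the qualifying bilirubin sample. Checking ALP only at the elevation would label a later cholestatic rise, with bilirubin and ALP both high, as Hy's Law. That is foreseeable in a study open to cholangiocarcinoma.

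The cost is SAP wording, one derivation and one extra row per category, using data already collected. No visit or sample is added. A few unrelated late bilirubin rises will be flagged for review. The 34-day window still leaves gaps: EOT to Safety Follow-up can reach 37 days, and an EOT panel can lie beyond 34 days when the last dose is 25 or more days after the last Day 1 draw (25 + 10 = 35). A table footnote should say so.
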